## 10. SAFETY

### 10.1 Drug studies

During the entire duration of the study, all adverse events (AE) and all serious adverse events (SAEs) are collected, fully investigated and documented in source documents and case report forms (CRF). Study duration encompassed the time from when the participant signs the informed consent until the last protocol-specific procedure has been completed, including a safety follow-up period. For adverse event the information collected are: time of onset, duration, resolution, action to be taken, assessment of intensity, relationship with study treatment. The evaluations will be done during the hospital stay and the further planned clinical evaluations.

#### 10.1.1 Definition and assessment of (serious) adverse events and other safety related events

An Adverse Event (AE) is any untoward medical occurrence in a patient or a clinical investigation participant administered a pharmaceutical product and which does not necessarily have a causal relationship with the study procedure. An AE can therefore be any unfavourable and unintended sign (including an abnormal laboratory finding), symptom, or disease temporally associated with the use of a medicinal (investigational) product, whether or not related to the medicinal (investigational) product.

A Serious Adverse Event (SAE) is classified as any untoward medical occurrence that:

- results in death,
- is life-threatening,
- requires in-patient hospitalization or prolongation of existing hospitalisation,
- results in persistent or significant disability/incapacity, or
- is a congenital anomaly/birth defect.

In addition, important medical events that may not be immediately life-threatening or result in death, or require hospitalisation, but may jeopardise the patient or may require intervention to prevent one of the other outcomes listed above should also usually be considered serious.

SAEs will be followed until stabilisation. Participants with ongoing SAEs at study termination (including safety visit) will be further followed up until stabilisation of the disease after termination.

The Principal Investigator will be informed on the randomization and will be available 24/24 hours, 365 days/year in case of complications related to the pudendal nerve block occur.

#### Assessment of Causality

The Sponsor-investigator make a causality assessment of the event to the study drug, based on the criteria listed in the ICH E2A guidelines:

Relationship	Description
Definitely	Temporal relationship Improvement after dechallenge* Recurrence after rechallenge (or other proof of drug cause)
Probably	Temporal relationship Improvement after dechallenge No other cause evident

Possibly	Temporal relationship Other cause possible
Unlikely	Any assessable reaction that does not fulfil the above conditions
Not related	Causal relationship can be ruled out
*Improvement after dechallenge only taken into consideration, if applicable to reaction	

### Unexpected Adverse Drug Reaction

An “unexpected” adverse drug reaction is an adverse reaction, the nature or severity of which is not consistent with the applicable product information (e.g. Investigator’s Brochure for drugs that are not yet approved and Product Information for approved drugs, respectively).

### Suspected Unexpected Serious Adverse Reactions (SUSARs)

The Sponsor-Investigator evaluates any SAE that has been reported regarding seriousness, causality and expectedness. If the event is related to the investigational product and is both serious and unexpected, it is classified as a SUSAR.

### Assessment of Severity

Grade refers to the severity of the AE. The CTCAE displays Grades 1 through 5 with unique clinical

descriptions of severity for each AE based on this general guideline:

- Grade 1 Mild; asymptomatic or mild symptoms; clinical or diagnostic observations only; intervention not indicated.
- Grade 2 Moderate; minimal, local or noninvasive intervention indicated; limiting age-appropriate instrumental activity day living.
- Grade 3 Severe or medically significant but not immediately life-threatening; hospitalization or prolongation of hospitalization indicated; disabling; limiting self-care activity day living.
- Grade 4 Life-threatening consequences; urgent intervention indicated.
- Grade 5 Death related to AE.

For a detailed description of EAs, we follow the CTCAE Version 4.03 - June 14, 2010^12.

### 10.1.2 Reporting of serious adverse events (SAE) and other safety related events

#### Reporting of SAEs

All SAEs will be reported immediately and within a maximum of 24 hours to the Sponsor-Investigator of the study. SAEs resulting in death are reported to the local Ethics Committee (via local Investigator) within 7 days.

#### Reporting of SUSARs

A SUSAR needs to be reported to the local Ethics Committee (local event via local Investigator) and to Swissmedic for category B and C studies (via Sponsor-Investigator) within 7 days, if the event is fatal, or within 15 days (all other events).

#### Reporting of Safety Signals

All suspected new risks and relevant new aspects of known adverse reactions that require safety-related measures, i.e. so-called safety signals, must be reported to the Sponsor-Investigator within 24 hours. The Sponsor-Investigator must report the safety signals within 7 days to the local Ethics Committee

#### Periodic reporting of safety

An annual safety report is submitted once a year to the local Ethics Committee via local Investigator

### **10.1.3 Follow up of (Serious) Adverse Events**

In case of SAE the patient will be followed up according the type and the severity of the complication developed, at least until stabilization.

## **11. STATISTICAL METHODS**

### **11.1 Hypothesis**

The hypothesis to be tested is that the spinal anaesthesia + pudendal nerve block is superior to the spinal anaesthesia alone in terms of postoperative pain.

### **11.2 Determination of Sample Size**

Based on previous studies we will expect a 33% reduction in VAS scale. To detect a clinically relevant difference between groups with a type I error of 0.05 and a power of 0.80 we determined a sample size of 18 subjects per group. Taken into account a possible drop out for different reasons of 10% we calculated the definitive sample size in 20 patients per group.

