## **5. STUDY OUTCOMES**

### **5.1 Primary Outcome**

Postoperative pain measured on VAS scale at 6, 12, 24, 48 hours

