### **11.3 Planned Analyses**

Descriptive statistics will be presented as mean with standard deviation (SD) or as median with interquartile range (IQR) for quantitative data. Qualitative data will be presented as absolute numbers with percentages. Comparisons of postoperative pain measured on VAS scale at 6, 12 and 24 h after surgery between group A and group B will be performed with the non-parametric repeated measures analysis of variance (Friedman test). By statistically significant p-value, post-hoc tests will be performed taken into account the multiple comparisons. Qualitative data between groups of patients will be compared with the Chi-Square test, or the Fisher exact test as appropriate. By statistically significant result post-hoc comparisons were made with the appropriate critical level adjustment. Comparisons of quantitative data between groups will performed with the Student's t-test or with the Mann-Whitney test as appropriate. All tests will be conducted two-sided, and p-values < 0.05 will be considered statistically significant. Stata version 12.1 (StatCorp. LP, College Station, TX, USA) will be used for all statistical analysis.

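### The 80% power in 11.2 cannot be reproduced and is not tied to the primary analysis in 11.3, for which no success rule is stated

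*Combined protocol and SAP*

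**What the plan says.** Section 11.2 (repeated in the synopsis) holds the only sample size calculation. The effect is "Based on previous studies we will expect a 33% reduction in VAS scale". The aim is "To detect a clinically relevant difference between groups", and "with a type I error of 0.05 and a power of 0.80 we determined a sample size of 18 subjects per group". The last step is "Taken into account a possible drop out for different reasons of 10% we calculated the definitive sample size in 20 patients per group". No SD, control mean, test, time point or alpha adjustment is given.

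Section 5.1 defines the primary outcome as "Postoperative pain measured on VAS scale at 6, 12, 24, 48 hours", with no lead time.

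Section 11.3 covers "Comparisons of postoperative pain measured on VAS scale at 6, 12 and 24 h after surgery between group A and group B", so 48 h is not among the analysed times. It assigns these comparisons to a Friedman test. If that is significant, "post-hoc tests will be performed taken into account the multiple comparisons"; neither the contrasts nor the correction is named. It adds that "All tests will be conducted two-sided, and p-values < 0.05 will be considered statistically significant". A separate, general sentence gives the t-test or Mann-Whitney test for quantitative data between groups, without assigning it to VAS.

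Section 11.1 states a superiority hypothesis on postoperative pain but does not say which result would establish it.

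**The concern.** A power figure describes one test of one hypothesis at one alpha. Section 11.2 reads like a single comparison at 0.05. Section 11.3 describes a gate followed by several adjusted tests, over a set of times that differs from 5.1. Nothing links the two.

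The ethics committee and later readers will take 80% as the trial's chance of detecting the expected benefit. A negative result from 36 to 40 patients would then be read as evidence against the block from an adequately powered trial, although the power of the actual procedure was never worked out. A mixed result, significant at one time and not at others, could be read either way because no success rule exists.

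**Working it through.** **1. The plan's own figures.** The dropout step reproduces: 18 / (1 - 0.10) = 20 per group. The 18 does not, because the SD is missing. With the normal approximation, n per group = 2 × (1.960 + 0.842)² × (SD / difference)². Taking the difference as 0.33 of the control mean and assuming a range for the SD (none is in the documents):

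| SD / control mean (assumed) | n per group for 80% |
|---|---|
| 0.30 | 13 |
| 0.35 | 18 |
| 0.40 | 24 |
| 0.50 | 37 |

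**2. What 18 implies.** Assume one two-sample t-test at two-sided 0.05. Power comes from the noncentral t with 2n - 2 degrees of freedom and noncentrality d × √(n/2). For n = 18, power 0.80 needs d = 0.961 (noncentrality 0.961 × 3 = 2.88, critical value 2.03). The implied SD is 0.33 / 0.961 = 0.343 of the control mean. The normal approximation gives d = 0.934 and Mann-Whitney 0.985, so the choice of test matters little. The unstated SD matters more: at 0.40 or 0.50 of the control mean, the same single test with 18 per arm has 67% or 49% power.

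**3. Adjusted tests at each time.** Assume that the post-hoc tests compare the arms at each time, with Bonferroni and d = 0.961 throughout.

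| Times tested | Alpha per test | 18 per arm | 20 per arm |
|---|---|---|---|
| 3 (11.3) | 0.0167 | 64.4% | 70.2% |
| 4 (5.1) | 0.0125 | 60.0% | 66.2% |

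Mann-Whitney gives 64.3% and 59.9% with 18 per arm. Holm, simulated with equal effects at every time and correlation 0.5-0.7, gives about 72-73% over three times and 69-70% over four.

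**4. Dependence on the success rule.** Simulation with 18 per arm, Bonferroni, equal effects and within-patient correlation 0.5-0.7 (assumed):

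| Rule | 3 times | 4 times |
|---|---|---|
| Significant at every time | 40-46% | 28-36% |
| Significant at one given time | 64% | 60% |
| Significant at one or more times | 82-87% | 82-88% |

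**5. The gate.** Steps 3 and 4 ignore the Friedman test, which ranks each patient's own scores over time and does not compare the arms. In 2,000 simulated trials (36 patients pooled, three times, correlation 0.5) with a constant group difference of d = 0.961 and no time trend, it rejected in 5%, which is its type I error rate. With a time trend it could reject often, with or without a treatment effect. Its effect on overall power is unknown and may go either way.

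**6. A single contrast.** For the mean of K times with common SD and correlation r, the standardised difference is d / √[(1 + (K - 1)r) / K].

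| Contrast, 18 per arm, two-sided 0.05 | r = 0.5 | r = 0.7 |
|---|---|---|
| Mean of 3 times | 1.177, power 93% | 1.075, power 88% |
| Mean of 4 times, effect at all | 1.216, power 94% | 1.092, power 89% |
| Mean of 4 times, no effect at 48 h (× 3/4) | 0.912, power 76% | 0.819, power 67% |

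The last row matters because section 3.2 describes the analgesic effect as lasting up to 24 hours.

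**The case against.** A reader might infer that the trial simply has 60-64% power instead of 80%. The documents do not support that. Those figures are for one given time and rest on Bonferroni-adjusted between-group tests, which 11.3 does not name. Under a rule of at least one significant time, power is 82-88%, at or above the stated level. With all 20 per arm, or with Holm, the per-time figures rise, though they stay below 80%. The 60% end also needs four tested times, while 11.3 analyses three.

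A reader might also infer that the 80% belongs to a test absent from the plan. That goes too far as well. Section 11.2 names no test, so a single unadjusted t-test is an inference. Section 11.3 does contain an unadjusted two-group test for quantitative data; what is missing is its assignment to VAS at a chosen time or summary.

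The total is itself unclear: 6.1 speaks of 100 patients, and 50 per arm would give about 99% per time point over three or four times on the same assumptions. That discrepancy must be reconciled separately. The calculation here follows 11.2, which is the stated basis for the sample size.

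These objections limit what the figures can claim. They leave untouched that 18 cannot be verified, that the 0.80 is not linked to the 11.3 procedure, and that no success rule is written.

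**Conclusion.** The point holds as one of unstated inputs and an unlinked analysis. No arithmetic error is shown, and the dropout step is correct. No single figure can replace the 0.80, because the power of the 11.3 procedure depends on a success rule, a correction and a set of contrasts that are not given, and on a gate that does not test the treatment effect.

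The size is therefore conditional. If 11.2 assumed one unadjusted two-sided t-test, power ranges from about 28% to 88% with 18 evaluable per arm, according to the success rule and the number of times. This rests on d about 0.96 at every time, Bonferroni, and an assumed correlation of 0.5-0.7. It should be corrected, and that can be done within the planned sample size.

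**What to change.** **In 11.3**, replace the Friedman-then-post-hoc procedure with one pre-specified between-group primary contrast, tested once at two-sided 0.05. One example is each patient's mean VAS over a stated set of times. Other single contrasts, such as VAS at one named time, would also be valid. Say explicitly whether 48 h is included, align 5.1 with 11.3, and make the per-time comparisons secondary.

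**In 11.2**, state the assumed control mean, SD and within-patient correlation with their source, name the test, and give its power. If the mean is chosen, the figures in step 6 show what to expect: about 88-93% for three times and 89-94% for four, or 67-76% if 48 h is averaged in and has no effect. If that last case is plausible, its figure should be stated.

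**Cost.** Wording only, with no added patients under the implied assumptions. Time-specific results become secondary, and the stated power may be less favourable once a real SD is entered. If the per-time tests were kept as primary instead, 80% at each time under Bonferroni would need 25 (three times) or 26 (four times) evaluable patients per arm.

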### **11.3 Planned Analyses**

Descriptive statistics will be presented as mean with standard deviation (SD) or as median with interquartile range (IQR) for quantitative data. Qualitative data will be presented as absolute numbers with percentages. Comparisons of postoperative pain measured on VAS scale at 6, 12 and 24 h after surgery between group A and group B will be performed with the non-parametric repeated measures analysis of variance (Friedman test). By statistically significant p-value, post-hoc tests will be performed taken into account the multiple comparisons. Qualitative data between groups of patients will be compared with the Chi-Square test, or the Fisher exact test as appropriate. By statistically significant result post-hoc comparisons were made with the appropriate critical level adjustment. Comparisons of quantitative data between groups will performed with the Student's t-test or with the Mann-Whitney test as appropriate. All tests will be conducted two-sided, and p-values < 0.05 will be considered statistically significant. Stata version 12.1 (StatCorp. LP, College Station, TX, USA) will be used for all statistical analysis.

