	
The pudendal nerve block with local anaesthetic is effective to reduce the postoperative pain for up to 24 hours. Currently no randomized study compares the effectiveness of perianal nerve blocks as adjuvant to spinal anaesthesia in the management of postoperative pain in patients undergoing hemorrhoidectomy. On the other hand, the pudendal nerve block procedure is safe, economic and simple. Complications related to the procedure such as intravenous injection of the anaesthetic, the formation of a retroperitoneal hematoma or abscess of the psoas muscle are described, although extremely rare.
 
The aim of this prospective randomized double-blind study is to compare the postoperative pain in patients undergoing Milligan Morgan hemorrhoidectomy under spinal anaesthesia with or without the pudendal nerve block.

Objective(s):	The objective is to assess the efficacy of the pudendal nerve block in patients treated by hemorrhoidectomy under spinal anaesthesia
Outcome(s):	
Primary outcome:
 
 
• Postoperative pain measured on VAS scale at 6, 12, 24, 48 hours
 
 
Secondary outcomes:
 
 
• Antalgic drugs as needed (opioids needed)
 
• Length of hospital stay
 
• Safety of the pudendal nerve block
 

Study design:	Randomized control single-blind trial
Inclusion / Exclusion criteria:	
Inclusion criteria:
 
 
• Patients affected by haemorrhoids (grade III and IV) and treated with Milligan-Morgan hemorrhoidectomy under spinal anaesthesia
 
• Signed informed consent
 
 
Exclusion criteria:
 
 
• Age < 18 year-old
 
• Pregnancy
 
• Allergy to local anaesthetics
 

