Measurements and procedures:	
Patients' clinical data and operative time will be collected
 
Patients selected will be randomized in two groups.
 
 
• Group A will undergo Milligan-Morgan hemorrhoidectomy under pudendal nerve block plus spinal anaesthesia
 
• Group B will undergo Milligan-Morgan hemorrhoidectomy under spinal anaesthesia
 
 
The randomization list will be created by the CTU-EOC and the randomization will be performed by the authorized personnel (physician responsible for the study, the anaesthetist and the surgeons) of the participating centre via RedCap®. Only the physician responsible for the study, the anaesthetist and the surgeons will be informed about the treatment arm.

	
After the operation all the patient will receive Metronidazole 500 mg x3 + Paracetamol 1 gr x4 + NSAID + opioids as needed for at least 48 hours. The postoperative pain will be evaluated at 6, 12, 24, 48 hours with VAS scale both as in-patients or out-patients on specific formularies. In-patients will be then controlled after 1 months, while out-patients after 1 and 4 weeks.
 
Results will be collected on specific printed Case report form. The Principal Investigator will preserve the sensitive data in his office in a closed cabinet key. Results will be then collected on a Redcap® electronic database. The access to the database will require username and password. Only the authorized personnel (physicians responsible for the study) will have the access rights and all changes on the database are trackable.

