#### **3.2 Clinical Evidence to Date**

The pudendal nerve block with local anaesthetic is effective to reduce the postoperative pain for up to 24 hours. Currently no randomized study compares the effectiveness of perianal nerve blocks as adjuvant to spinal anaesthesia in the management of postoperative pain in patients undergoing hemorrhoidectomy. On the other hand, the pudendal nerve block procedure is safe, economic and simple. Complications related to the procedure such as intravenous injection of the anaesthetic, the formation of a retroperitoneal hematoma or abscess of the psoas muscle are described, although extremely rare.

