### **5.2 Secondary Outcomes**

Antalgic drugs as needed (type of drug and number of administrations)

Length of hospital stay (days)

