#### **11.3.2 Primary Analysis**

The primary analyses will be conducted at the end of the study by [name] [name], OBV (Chief of the EOC Biostatistic Service)

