#### **12.1.2 Specification of source documents**

Source data on the CRF include the original documents relating to the study, as well as the medical treatment and medical history of the participant (demographic data, clinical data, participation in study and Informed Consent, VAS scale at 6, 12, 24, 48, drugs taken, length of hospital stay, complications).

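### The primary outcome is VAS pain at 6, 12, 24 and 48 h, but the only planned VAS comparison stops at 24 h, so 48 h has no designated primary test

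*Combined protocol and SAP*

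**What the plan says.** The synopsis states the primary outcome as "Postoperative pain measured on VAS scale at 6, 12, 24, 48 hours". Sections 5.1 and 9.2.1 give the same four times. Data collection matches: under measurements and procedures the synopsis says "The postoperative pain will be evaluated at 6, 12, 24, 48 hours with VAS scale", sections 6.1 and 6.2.2 repeat the four times, and section 12.1.2 lists as source data "VAS scale at 6, 12, 24, 48, drugs taken, length of hospital stay, complications".

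The analysis text differs. Section 11.3, and the synopsis entry on statistical considerations in the same words, plans "Comparisons of postoperative pain measured on VAS scale at 6, 12 and 24 h after surgery" between groups A and B by the Friedman test, followed by post-hoc tests that allow for multiple comparisons. The adjustment method and the number of comparisons are not given.

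Three other places might have settled the status of 48 h:

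- Section 5.2 lists as secondary outcomes "Antalgic drugs as needed (type of drug and number of administrations") and length of hospital stay. VAS at 48 h is not among them.
- Section 11.3.2, headed as the primary analysis, opens "The primary analyses will be conducted at the end of the study by" and then identifies the analyst. It names no endpoint, time or test.
- Section 11.3 also has a general rule: "Comparisons of quantitative data between groups will performed with the Student's t-test or with the Mann-Whitney test as appropriate". It mentions neither VAS nor 48 h.

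**The concern.** Section 5.1 supports a primary result over 6-48 h; section 11.3 supports one over 6-24 h. With both in force, the analyst could pick either after seeing the data and cite the protocol for it.

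The time left out is not a neutral one. Section 3.2 describes the block as "effective to reduce the postoperative pain for up to 24 hours", so 48 h is where the protocol's own rationale expects least effect. Leaving it out would tend to favour the block if the effect has faded by then. The number of post-hoc comparisons to adjust for, three or four, is also undefined.

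**Working it through.** **1. Time points side by side**

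| Place | Times |
|---|---|
| Primary outcome: synopsis, 5.1, 9.2.1 | 6, 12, 24, 48 h |
| Collection: synopsis, 6.1, 6.2.2, 12.1.2 | 6, 12, 24, 48 h |
| Planned VAS comparison: synopsis, 11.3 | 6, 12, 24 h |
| Secondary outcomes: 5.2 | VAS not listed |
| Primary analysis: 11.3.2 | none named |

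Four times are declared and three are compared. The one missing is 48 h, in both places that describe the analysis.

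**2. Share of the data**

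At 20 per group (section 11.2): 40 patients × 4 = 160 planned VAS values, of which 40 are at 48 h; 40/160 = 25%. At the 100 patients given in section 6.1: 100/400 = 25%. The conflict between those two sample sizes does not affect the share.

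**3. The plan's own sample-size figure**

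The step from 18 to 20 per group reproduces: 18/(1 − 0.10) = 20. The 18 itself cannot be reproduced, because section 11.2 gives a 33% reduction but no SD, control mean or time point. Working backwards at two-sided 0.05 and 80% power, the standardised difference is d = (1.960 + 0.842) × √(2/18) = 0.934 by the normal approximation, or 0.961 by noncentral t.

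**4. Illustration: three times or four**

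This is an assumed analysis, not the planned test. Each patient's VAS is averaged over time and the group means are compared. Assumptions: 18 per group, equal SDs, equal correlation r between times, effect d = 0.934 at 6, 12 and 24 h, and effect f × d at 48 h.

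- Three times: standardised effect = d / √((1 + 2r)/3)
- Four times: standardised effect = d × (3 + f)/4 / √((1 + 3r)/4)
- Power = Φ(effect × √(18/2) − 1.960)

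For r = 0.5, three times: 0.934/√0.667 = 1.144; 1.144 × 3 − 1.960 = 1.47; power 92.9%. For four times with f = 0: 0.934 × 0.75/√0.625 = 0.886; 0.886 × 3 − 1.960 = 0.70; power 75.7%.

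| r | Three times | Four, f = 0 | Four, f = 0.5 | Four, f = 1 |
|---|---|---|---|---|
| 0.3 | 97.0% | 86.2% | 94.5% | 98.2% |
| 0.5 | 92.9% | 75.7% | 87.3% | 94.3% |
| 0.7 | 87.9% | 66.5% | 79.5% | 88.9% |

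Using the t distribution throughout, with d = 0.961, changes these by no more than 0.1 point.

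**5. Illustration: post-hoc thresholds**

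Section 11.3 names no adjustment method, so Bonferroni is assumed. The threshold is 0.05/3 = 0.0167 for three times and 0.05/4 = 0.0125 for four. Power per time point at the back-solved effect falls from 65.8% to 61.9% (normal) or from 64.4% to 60.0% (t).

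**The case against.** The mismatch itself is not in dispute. The case against concerns how much to make of it.

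- *No test is labelled primary at any time point, and the general t-test/Mann-Whitney rule covers 48 h.* This is partly right: section 11.3 never uses the word primary, and the general rule could be applied at 48 h. But the Friedman sentence is the only one that gives VAS a test, and VAS is the primary outcome. Under the general rule, one of four primary time points would be tested by a different method, outside the stated post-hoc adjustment.
- *The power figures do not measure the defect.* This stands. They rest on an unplanned test, a back-solved effect and assumed correlations, and even the direction varies: from a loss of 21.4 points (r = 0.7, f = 0) to a gain of 1.4 (r = 0.5, f = 1). They show only that the choice can move the result.
- *Making 48 h secondary with a named test would also cure the inconsistency.* It would, but it would change an outcome declared primary in three places instead of following it.
- *Adding 48 h has hidden costs.* Section 11.4 drops patients with missing data, and a missing 48 h form might then remove a patient's earlier scores. That rule applies to missing data whether or not 48 h is added. Separately, the synopsis gives a 48-hour minimum for background analgesia and section 8.1.2 gives 24. That affects how a 48 h comparison is read, and the two statements must be reconciled.

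**Conclusion.** The concern holds. Followed as written, section 11.3 leaves one of four declared primary time points (25%) out of the only VAS comparison, and no other section resolves it. This rests on the current text alone and needs no assumption.

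The consequence is an open choice between two results after the data are seen, at the time where the protocol's rationale expects least benefit. No biased estimate is demonstrated, and the documents do not show whether the omission is a slip or deliberate. How far the choice could move the result depends on the assumptions above; at correlation 0.5, four-time power is 17.2 points lower to 1.4 points higher than with three times. It should be corrected before analysis, but it does not invalidate the trial.

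**What to change.** Before any comparison by arm, list all four times, 6, 12, 24 and 48 h, in the VAS comparison in section 11.3 and in the synopsis entry on statistical considerations. Include 48 h in the primary between-group comparison, and count four time points in the post-hoc multiplicity adjustment.

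The change is one phrase in two places, plus the sponsor and ethics committee approval that section 2.3 requires. No new data are needed. The price is a possibly less favourable primary result if the effect has faded by 48 h, and a slightly stricter post-hoc threshold (0.0125 instead of 0.0167 if Bonferroni is used).

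This removes the time-point ambiguity only. Whether the Friedman test can compare two independent groups must be settled separately.

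### The Friedman test named for the A-versus-B pain comparison does not test the between-group superiority hypothesis

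*Combined protocol and SAP*

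**What the plan says.** Section 11.1 states one hypothesis, and it is between groups: "spinal anaesthesia + pudendal nerve block is superior to the spinal anaesthesia alone in terms of postoperative pain". The primary outcome in 5.1 is "Postoperative pain measured on VAS scale at 6, 12, 24, 48 hours".

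Section 11.3, repeated in the synopsis under Statistical Considerations, covers "Comparisons of postoperative pain measured on VAS scale at 6, 12 and 24 h after surgery between group A and group B" and says that the comparison "between group A and group B will be performed with the non-parametric repeated measures analysis of variance (Friedman test"). It continues: "By statistically significant p-value, post-hoc tests will be performed taken into account the multiple comparisons". Later in the same paragraph is a general sentence: "Comparisons of quantitative data between groups will performed with the Student's t-test or with the Mann-Whitney test as appropriate". That sentence is not tied to VAS, to a time point or to the primary outcome.

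Section 11.3.2, headed Primary Analysis, gives only the timing and the person responsible. No section names a group term, a summary measure or a primary time point. The sample size in 11.2 is set "To detect a clinically relevant difference between groups with a type I error of 0.05 and a power of 0.80".

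**The concern.** The Friedman test is for related samples. Here the related values are the repeated VAS scores within a patient, while A and B are different patients. The test assigned to the primary outcome therefore answers whether pain changes between 6 and 24 h. The trial asks whether the block lowers pain.

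Three things are at stake.

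- A significant primary result could arise only because pain changes after surgery in both groups.
- If group comparisons are run only after a significant Friedman result, the chance of detecting a real benefit depends on the shape of the pain course.
- Because a general t-test/Mann-Whitney sentence stands beside the Friedman sentence, the text would allow a different primary test to be adopted after the data are seen. Nothing suggests that this is intended, but the plan does not rule it out.

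**Working it through.** **The plan's own figures.** The dropout step reproduces: 18 / (1 − 0.10) = 20 per group. The 18 cannot be reproduced, because no control mean, SD or test is given. Solving backwards for 80% power at two-sided 0.05:

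- Normal formula: d = √(2/18) × (1.960 + 0.842) = 0.934. The t-test version is 0.961.
- If the control mean were 5 (assumed), a 33% reduction is 0.33 × 5 = 1.65, and the implied SD is 1.65 / 0.961 = 1.72.
- By the normal formula, the implied SD is 1.41, 1.77, 2.12 or 2.47 for control means of 4, 5, 6 or 7.

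This power refers to a difference between groups, so it does not carry over to the Friedman test.

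**Layout 1: patients as blocks, times as treatments.** Q = 12 / [b·k·(k+1)] × ΣR² − 3b(k+1), where b is the number of patients, k = 3 times and R are the rank sums per time. Ranks are taken within each patient, so subtracting a constant from every group A value changes none of them. In a numerical check, subtracting 0, 1, 5 or 100 gave Q = 1.80 each time.

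**Layout 2: times as blocks, one summary value per group (k = 2).** The most extreme result is A lower at all three times, with rank sums 3 and 6: Q = 12/(3·2·3) × (9 + 36) − 3·3·3 = 30 − 27 = 3. This gives p = 0.083 by chi-square and 2 × 0.5³ = 0.25 exactly, so 0.05 cannot be reached. Adding 48 h gives a maximum Q of 12/(4·2·3) × (16 + 64) − 3·4·3 = 4, with p = 0.046 by chi-square but 0.125 exactly.

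**Layout 3: times as blocks, all patients as replicates.** This has a group factor and can reach 0.05, but it treats repeated values on one patient as independent. Simulated type I error was 0.15 to 0.17.

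**Size of the effect on the trial.** None of these inputs is in the documents: 18 per group; control mean 5; SD 1.72; within-patient correlation 0.5; normal VAS clipped to 0–10; linear fall from 6 through 12 to 24 h; 10,000 simulated trials per scenario; Friedman on the pooled 36 patients. The plan does not name its post-hoc tests, so they are taken as Bonferroni-adjusted Mann-Whitney tests of A versus B at each time. Gated means counted only when Friedman is significant. The fading effect is 1.65, 0.825 and 0 at 6, 12 and 24 h. It is an assumption prompted by section 3.2: "The pudendal nerve block with local anaesthetic is effective to reduce the postoperative pain for up to 24 hours".

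| Block effect | Fall 6–24 h | Friedman rejects | Gated | Ungated | MW on mean VAS | MW at 6 h only |
|---|---|---|---|---|---|---|
| None | 0 / 1 / 2 | 5% / 74% / >99% | – | – | 5% / 5% / 5% | – |
| Constant 1.65 | 0 / 1 / 2 | 5% / 75% / >99% | 4% / 63% / 83% | 84% / 84% / 83% | 91% / 92% / 91% | – |
| Fading | 0 / 1 / 2 | 50% / 5% / 82% | 30% / 3% / 50% | 61% / 62% / 61% | 38% / 37% / 38% | 76% / 77% / 77% |

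The first two rows show the fault: the Friedman rejection rate follows the fall in pain and is the same with or without a constant block effect. In the fading case with a 1-point fall, pain falls by 1 in B and rises by 0.65 in A. The two trends nearly cancel in the pooled ranks, and Friedman rarely rejects.

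For Mann-Whitney on mean VAS with a constant effect, power runs from about 50% to over 99% across SD 1.25–2.5 and correlation 0.2–0.8.

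**The case against.** The best defence is that the plan does contain between-group tests. VAS is quantitative, so the t-test/Mann-Whitney sentence could literally cover it, and the post-hoc tests could be read as A versus B at each time. It may also be that a factorial rank method with a group factor was meant, since the layout is not stated. On that view the fault is loose wording.

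Part of this stands. A valid comparison could still be run, and if pain falls steeply the Friedman condition will usually be met. But VAS has its own named test in the same paragraph, the general sentence is not assigned to it, and the post-hoc tests are unnamed and conditional. If another method was meant, the text must still be corrected. The one Friedman layout that has a group factor and can reach 0.05 does not hold its type I error.

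A second objection is that the power losses rest on assumed inputs and on flat or falling pain only. This is fair: the figures illustrate a range and are not an estimate for this trial. With the fading effect and pain rising by 1 or 2 points, gated and ungated power are both about 63%, so nothing is lost. A rising course does not remove the loss for a constant effect, however, because Friedman ignores the direction of the trend.

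Third, the omission of 48 h from 11.3 and the missing control mean and SD in 11.2 are separate defects. They appear here only because the corrected test cannot be written without settling them, and they add nothing to the severity of this point.

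**Conclusion.** The concern holds and must be fixed before analysis. The only test assigned to the primary outcome does not validly test the trial's only stated hypothesis. With patients as blocks it has no group term. With times as blocks it either cannot reach 0.05 or has a type I error of about 0.15 to 0.17. This conclusion needs no numerical assumption, apart from the simulated type I error of the replicated layout.

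The practical loss does depend on assumptions. Under those listed, the loss of power from the Friedman condition runs from none to nearly total (84% down to 4% for a constant effect with flat pain). The chance that Friedman is significant with no block effect runs from about 5% to over 99%.

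**What to change.** 1. In 11.3 and the synopsis, replace the Friedman sentence with one between-group primary test at two-sided 0.05. Since the plan prefers a non-parametric method, one option is: *Mann-Whitney test of A versus B on each patient's mean (or AUC) VAS over [stated time points], with the Hodges-Lehmann estimate of the difference and its 95% CI.* A mixed-model group contrast averaged over the same times is an acceptable alternative. Name only one.
2. State the time points, and make 5.1, 11.3 and the synopsis agree on 48 h. The choice matters: mean VAS over 6, 12 and 24 h has about 91% power for a constant effect but about 37% for the fading one, against about 77% at 6 h alone.
3. Say how a missing time point enters the patient's summary value. Section 11.3.1 includes all randomised patients, while 11.4 drops those with missing data.
4. Make comparisons at single time points secondary and Holm-adjusted, and run them whatever any test of change over time shows.
5. Limit the general t-test/Mann-Whitney sentence to secondary outcomes.
6. In 11.2, restate the calculation for the chosen test with its control mean, SD and, if values are averaged, the within-patient correlation.

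**Cost.** Amended wording in 11.2, 11.3 and the synopsis, and one recalculation, with the same data and visits. The number of patients changes only if the recalculation requires it. For mean VAS over three times, the SD of the mean is SD × √((1 + 2ρ)/3), and the t-test n is divided by 0.955 for Mann-Whitney. For a difference of 1.65:

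- SD 1.25, ρ 0.2: SD of the mean 0.854, d = 1.93, about 6 per group.
- SD 2.5, ρ 0.8: SD of the mean 2.327, d = 0.709, about 34 per group.
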